12.2 Dose Modification

The dose and administration of the study drug to any patient within a cohort may not be modified. If necessary, a patient must be discontinued for the reasons described in [Section 11.3](#).

12.3 Method of Assigning Patients to Treatment Groups

Each patient will be assigned a unique identification number upon screening. Patients who complete the study screening assessments and meet all the eligibility criteria will be assigned a unique randomization identification number at the time of dosing, different from the screening number, and will receive the corresponding product, according to a randomization scheme generated at Celerion.

Patients will be enrolled to Cohort 1 or Cohort 2 with Cohort 1 conducted prior initiation of Cohort 2. In each cohort, an attempt will be made to enroll at least 50% of females and at least 30% of a race/ethnicity minority group. An attempt will also be made to approximately match key characteristics, including sex, average age, and weight per cohort.

In each cohort, patients will be randomized to receive either xisomab 3G3 or placebo maintaining a 2:1 ratio

If replacement patients are used, the replacement patient number will be 100 more than the original (e.g., Patient No. 101 will replace Patient No. 1).

12.4 Blinding

This is a double-blind, placebo-controlled study.

12.4.1 Maintenance of Randomization

A computerized randomization scheme will be created by a Celerion statistician and it shall be considered blinded as per the following: the randomization is available only to the CRU pharmacy staff that is preparing the drug who will not be involved in any other aspect of the study including administration of the drug. It will not be made available to the Sponsor, patients, or members of the staff responsible for the monitoring and evaluation of safety assessments.

12.4.2 Procedures for Breaking the Blind Prior to Study Completion

One set of sealed envelopes containing the randomization code will be supplied to the PI or designee at the start of the study.

Breaking of the blind is expressly forbidden except in the event of a medical emergency where the identity of the drug must be known in order to properly treat the patient.

In the event of a medical emergency, it is requested that the PI or designee make every effort to contact the Study Monitor or designee prior to breaking the blind. If breaking the blind is required because of a medical emergency, the treatment identity would be revealed by the PI or designee, for that patient only. In the event that the emergency is one, in which it appears that the other patients may be at imminent risk, the blind may be broken for all patients dosed at that dose level. The unblinding will be properly documented in the study file.

In all cases where the code is broken, the PI or designee should record the date and reason for code breaking.

At the end of the study, envelopes will be retained or destroyed according to site procedures unless specified otherwise by the Sponsor.

12.4.3 Revealing of Randomization

In the absence of a medical emergency, the blinded randomization for this study will not be revealed until all data are entered in the database, edits checks are performed, queries closed, CRFs signed by the PI, and the database is officially locked.

12.5 Treatment Compliance

Drug administration will be performed by a qualified designee (e.g., nurse). Before and after IV infusion, the qualified designee will visually inspect the syringe to ensure that the patient has received the entire dose. In the case of an incomplete dosing a few milliliters of blood could be drawn back into the dosing syringe and carefully reinjected to ensure administration of the complete dose; this will be reported.

13 STUDY ASSESSMENTS AND PROCEDURES

The Study Events Flow Chart ([Section 6](#)) summarizes the clinical procedures to be performed at each visit. Individual clinical procedures are described in detail below. Additional evaluations/testing may be deemed necessary by the PI or designee and/or the Sponsor for reasons related to patient safety.

For this study, the primary assessment is the safety and tolerability. Safety will be determined by evaluating physical examinations, vital signs, ECGs, clinical laboratory parameters, including but not limited to, hematology, serum chemistry profile, coagulation, urinalysis, vascular access site reaction, and AEs as outlined in the Study Events Flow Chart ([Section 6](#)).

Any nonscheduled procedures required for urgent evaluation of safety concerns take precedence over all routine scheduled procedures.

13.1 Screening

Within 28 days prior to check-in on Day -8, medical history and demographic data, including name, sex, age, race, ethnicity, body weight (kg), height (cm), BMI (kg/m²) and history of tobacco use will be reported. Each patient will have a physical examination, vital sign measurements (heart rate, blood pressure, temperature, and respiratory rate), 12-lead ECG, and the laboratory tests of hematological, coagulation, hepatic and renal function and additional tests as noted in [Section 13.2.7](#).

13.2 Safety and Tolerability Assessments

13.2.1 Physical Examination

Full and abbreviated physical examinations will be performed as per Study Events Flow Chart ([Section 6](#)).

Full physical examinations will include, at a minimum, assessment of the following systems: skin, head, ears, eyes, nose and throat, respiratory system, cardiovascular system, gastrointestinal system, neurological condition, blood and lymphatic systems, and the musculoskeletal system.

Abbreviated physical examinations will include at the minimum, examination of respiratory, cardiovascular, and gastrointestinal systems, with the option for further examination of additional systems as necessary based on reported symptoms/AEs.

Symptom-driven physical examination may be performed at other times, if deemed necessary by the PI or designee.

Medical history will be recorded at screening.

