8.3.1 Safety Data

There were no deaths or SAEs experienced in this study. No subjects were discontinued due to AEs. Overall, 10 (48%) of 21 subjects experienced a total of 20 TEAEs in this study, with 7 (44%) of 16 subjects following active treatment and 3 (60%) of 5 subjects following placebo. The highest incidence of TEAEs by system organ class was skin and subcutaneous tissue disorders, experienced by 3 (19%) active-treatment subjects and 1 (20%) placebo subject. The most common TEAE in this study was productive cough, considered unrelated or unlikely treatment related and experienced by 2 (13%) active treatment subjects. All other TEAEs were experienced by 1 subject. The majority of events (17) were mild (Grade 1) in severity and 3 were moderate (Grade 2). Moderate events included increased diastolic BP (2 mg/kg xisomab 3G3), productive cough (5 mg/kg xisomab 3G3), and upper respiratory tract infection (0.5 mg/kg xisomab 3G3). As expected, increases from baseline in aPTT were noted following all treatments, with greater magnitude and duration of these increases following administration of the higher doses of xisomab 3G3.

A single IV dose of xisomab 3G3 up to 5 mg/kg appeared to be safe and generally well tolerated by the healthy male and female subjects in this study.

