8.5 Risks and/or Benefits to Patients

ESRD patients are often ill, and are prone to a variety of adverse events on or off HD, ranging, for example, from infections to hypertension to bleeding to thromboembolism to acute ischemic cardiovascular emergencies, even if they are apparently stable on chronic HD. A temporal and modest increase in blood pressure was observed in one study subject in the FIH study after xisomab 3G3 administration, and the event was deemed potentially related to the study drug.

Xisomab 3G3 is a purified protein produced by recombinant DNA technology in a mammalian cell culture system, and these types of drugs can, occasionally and unpredictably evoke acute allergic reactions. Some ESRD patients develop chronic HD- and uremia-related moderate hemorrhagic diathesis or hemostasis impairment. Even though currently available data do not indicate a hemostatic function for the FXI/FXII interaction, there remains a theoretical possibility of contact activation-mediated enhancement of hemostasis. Thus, the hemostatic safety of xisomab 3G3 in the complex conditions of ESRD and chronic HD is not yet known. The safety monitoring practices employed by this protocol (i.e., 12-lead ECG, vital signs, blood pressure, clinical laboratory tests, AE questioning, vascular access site (AV fistula or AV graft) monitoring, and physical examination) are adequate to protect the patients' safety and should detect all expected and unexpected treatment-emergent AEs (TEAEs). In addition, the cohorts will be dosed in a sequential manner, starting with the lower dose level, Cohort 1.

Patients undergoing heparin-free HD may be at higher risk of developing clots within the hemodialyzer. Should this occur, site standard operating procedures will be followed to replace the clotted dialyzer and resume HD under the supervision of the PI. It is important to note that replacement of the dialyzer cartridge is a safe procedure for the patient. While studies suggest that there is no risk of thromboembolic complications should this occur, clotting of the dialyzer circuit could result in up to ~228 mL of blood loss.

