9.2 Endpoints

Primary outcome measures:

- The safety and tolerability of xisomab 3G3 will be evaluated versus pre-treatment and placebo by reviewing number and severity of adverse events and use of concomitant medications, physical examination, vascular access site reaction, bleeding time, and changes in vital signs, ECGs, and clinical laboratory evaluations.

Secondary outcome measures:

- PD using dose-dependency of drug potency, determined by measuring changes in coagulation parameters, and thrombus accumulation (assessed and ranked by visual inspection) within the dialyzer cartridges and total protein accumulation in the HD filter after xisomab 3G3-treatment versus pre-treatment and placebo.
- Efficacy on hemodialysis efficiency using BUN and potassium levels before and after hemodialysis, length of HD, measurement of urea removed by 3 hours of dialysis, and total dialysate urea (single pool Kt/V and URR) after xisomab 3G3-treatment versus pre-treatment and placebo.

Other outcome measures:

- PK parameters of xisomab 3G3, calculated, as appropriate: AUC0-t, AUC0-inf, AUC%extrap, Cmax, Tmax, Kel, t^{1/2}, CL, and Vss.
- Development of immunity or antibodies against xisomab 3G3 after drug exposure.

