### **8.8 Physical Examination**

Full physical examinations will be performed at Screening and Day -8 check-in and abbreviated physical examination will be performed on Days 1, 6 and 12. Abnormal findings will be reported as medical history or adverse events. All data found in the CRF will be listed.

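### No physical examination scheduled after dosing is required to include the skin, so for skin the primary-outcome comparison rests on unscheduled observation or patient report

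*Protocol*

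**What the plan says.** Protocol 13.2.1 defines two examinations. For the longer one, "Full physical examinations will include, at a minimum, assessment of the following systems: skin", followed by seven further system groups that include blood and lymphatic. For the shorter one, "Abbreviated physical examinations will include at the minimum, examination of respiratory, cardiovascular, and gastrointestinal systems". Anything beyond these three systems is left to the examiner, "with the option for further examination of additional systems as necessary based on reported symptoms/AEs". Symptom-driven examinations are also allowed at other times, at the judgment of the principal investigator (PI) or designee.

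On timing, SAP 8.8 says "Full physical examinations will be performed at Screening and Day -8 check-in". For the shorter form it says "abbreviated physical examination will be performed on Days 1, 6 and 12". Footnote m of the Study Events Flow Chart (Protocol Section 6) places the Day 1 examination before dosing. Day 6 is discharge or early termination, and Day 12 is the follow-up visit.

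Protocol 9.2 counts "physical examination, vascular access site reaction, bleeding time, and changes in vital signs" among the components of the primary outcome, evaluated versus pre-treatment and placebo. Protocol 8.5 says that recombinant proteins of this kind "can, occasionally and unpredictably evoke acute allergic reactions", and that the hemostatic safety of the drug in patients with ESRD on dialysis is not yet known.

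**The concern.** Bruising, petechiae and rash are skin signs, and bleeding and allergy are among the harms this trial watches for. The plan requires the examiner to look at the skin before treatment but not after it. A painless bruise away from the access site, which the patient may not mention, need not be sought in any arm.

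What is at stake is how an absence of findings is read. The case for the drug is anticoagulation without added bleeding (Protocol 8.4.1). A report that no skin bleeding was seen would carry little weight if nobody had been required to look. Protocol 8.5 also lists physical examination among the practices that it expects to detect all treatment-emergent events, and the definition in Protocol 13.2.8.1 counts signs as well as symptoms as adverse events. Making the skin examination depend on reported symptoms or events sits uneasily with both.

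**Working it through.** No sample-size or error-rate figure bears on this, and the plan states no figure to reproduce. The check counts scheduled examinations against their required content.

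**Inputs.** Content: Protocol 13.2.1. Timing: Protocol Section 6 and SAP 8.8. Patients: 9 to 12 per cohort, two cohorts, 2:1 active to placebo (Protocol 10.1).

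**Step 1: schedule against content.**

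| Examination | Relative to dosing | Form | Skin required | Respiratory, cardiovascular, gastrointestinal required |
|---|---|---|---|---|
| Screening | before | full | yes | yes |
| Day -8 | before | full | yes | yes |
| Day 1 | before | abbreviated | no | yes |
| Day 6 | after | abbreviated | no | yes |
| Day 12 | after | abbreviated | no | yes |

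Skin is required in 2 of 3 predose and 0 of 2 post-dose examinations. The three core systems are required in 3 of 3 and 2 of 2, including the same abbreviated form on Day 1 predose. The abbreviated minimum keeps 3 of the 8 system groups, counting head, ears, eyes, nose and throat as one group.

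**Step 2: planned volume.** Patients: 2 × 9 = 18 to 2 × 12 = 24. Post-dose examinations if all complete: 18 × 2 = 36 to 24 × 2 = 48. At 2:1, each dose level has 6 to 8 patients and pooled placebo has 2 × 3 = 6 to 2 × 4 = 8. Each of the three groups therefore has 12 to 16 post-dose examinations, and none of these requires a look at the skin.

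**Step 3: the predose reference for skin.** Protocol 11.2 (criteria 2 and 3) allows unfractionated heparin during dialysis up to check-in on Day -8. Protocol 8.4.1 treats Days -7 to 1 as the heparin-free baseline. The last required skin examination therefore comes before the baseline that the design set up for comparison.

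**Step 4: what the other measures cover.**
- Access-site inspection (Protocol 13.2.5, SAP 8.9): the fistula or graft and surrounding area, at Day 1 predose and at the end of dialysis on Days 1, 3 and 5.
- Bleeding time (Protocol 13.2.6, SAP 8.10): puncture sites only, on Days -7, -5, -3, 1, 3, 5 and 12.
- Hematology, coagulation and platelets (SAP 8.4): do not record skin signs.
- Adverse event questioning (Protocol 13.2.8.2): patients are asked how they feel, once a day in confinement and at each return visit.

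None of these is a required look at the skin away from the access site.

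**Step 5: planned output.** SAP 8.8 sends abnormal findings to medical history or adverse events and lists the data. SAP 10.2 gives no physical-examination summary by treatment, although the heading of its Section 14.3.5 names physical examination.

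**The case against.** A shortened examination that is extended when symptoms call for it is a deliberate and common choice. Three stronger readings are tempting, and the documents support none of them.

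- *The examination cannot detect bleeding or allergy.* The three systems are a minimum, and symptom-driven examinations are allowed at any time. The required systems can themselves show respiratory or cardiovascular signs of allergy, or gastrointestinal bleeding. A sign seen by staff counts as an adverse event without any complaint from the patient (Protocol 13.2.8.1), and patients are in the unit from Day -8 to Day 6. Skin signs can be found, but nobody is required to look for them.
- *The component has no like-for-like pre-treatment comparison.* It has one for the three core systems on Day 1 predose. The gap covers only skin and the other systems left out of the abbreviated minimum.
- *Bleeding and allergy are the only harms named.* Protocol 8.5 also names a blood pressure rise and dialyzer clotting.

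Three further objections stand as limits on the point. First, other primary components address both harms directly, including vital signs one hour after dosing (SAP 8.5), so the gap is one of completeness. Second, the first-in-human result adds little. Protocol 8.3.1 says "The highest incidence of TEAEs by system organ class was skin and subcutaneous tissue disorders", but the rates were 3/16 = 19% on active and 1/5 = 20% on placebo, and the text does not say what the events were or how they were found. Third, timing limits the gain. Protocol 8.4.2 expects the lower dose to act for possibly up to a day, and reports an effect lasting at least 72 hours at the higher dose in healthy subjects. The first post-dose examination falls at about 120 hours, on Day 6.

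It is also true that no planned table fails because skin is omitted, since none is planned for any system. That lowers the severity. It does not supply the comparison that Protocol 9.2 describes.

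**Conclusion.** The point holds in a limited form and is minor. Skin is required in neither of the two post-dose examinations, in any arm. For skin, the comparison with pre-treatment and with placebo therefore rests on unscheduled observation or patient report. The other safety measures cover bleeding and allergy only in part.

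The count of 36 to 48 examinations assumes that all 18 to 24 patients complete. The value of a required look assumes that some bruising, petechiae or rash is still visible on Day 6 or Day 12 and would otherwise go unrecorded. The documents give no rate for this, so the number of findings missed cannot be estimated.

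**What to change.** In Protocol 13.2.1, add skin and visible mucosa to the abbreviated minimum on Day 1 predose, Day 6 and Day 12. Record bruising, petechiae, hematoma away from the access site, and rash, each as present or absent. The Day 1 entry supplies a same-form reference taken within the heparin-free period.

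In SAP 8.8, tabulate findings that are new since Day 1 predose, by dose level and pooled placebo.

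The cost is roughly a minute per examination (an estimate), one added entry on the case report form and one small table, with no extra visit or blood draw. More minor findings will be recorded in all arms.

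The change mainly serves bruising, petechiae and persistent rash. A transient acute rash between dosing and Day 6 would still depend on adverse event monitoring, because no physical examination is scheduled in that interval.

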13.2.2 Vital Signs

Single measurements of body temperature, respiratory rate, blood pressure, and heart rate, will be measured as outlined in the Study Events Flow Chart ([Section 6](#)). Additional vital signs may be taken at any other times, if deemed necessary.

Vital signs will be performed with patients in a seated position following a 5 minute rest period, except when they are supine or semi-reclined because of study procedures and/or AEs (e.g. nausea, dizziness) or if deemed necessary by the PI or designee.

When scheduled postdose, vital signs will be performed within approximately 15 minutes of the scheduled time point.

13.2.3 ECG Monitoring

Single 12-lead ECGs will be performed as outlined in the Study Events Flow Chart ([Section 6](#)). Additional ECGs may be taken at any other times, if deemed necessary by the PI or designee.

ECGs will be performed with patients in a semi-recumbent position following a 5 minute rest period. All ECG tracings will be reviewed by the PI or designee.

When scheduled postdose, ECGs will be performed within approximately 20 minutes of the scheduled time point.

13.2.4 Body Weight

Body weight (kg) will be measured daily up to Day 6, and before and after each HD session, as outlined in the Study Events Flow Chart ([Section 6](#)).

13.2.5 Vascular Access Site Reaction Assessment

The monitoring of AEs will pay special attention to vascular access fistula (or AV graft) site reactions. The preferred vascular access is an established AV fistula (or AV graft). Well established and reaction-free AV graft is an alternative, but less preferred access option, as it is more prone to complications. Patients who are hemodialyzed through catheters are not included in the study. Therefore, inspection of the AV fistula (or AV graft) and surrounding area will be performed. Any new abnormal findings inconsistent with past skin injuries as expected in patients on chronic HD will be reported as AEs. AV fistula (or AV graft) site reactions will be evaluated as outlined in the Study Events Flow Chart ([Section 6](#)). Prior to HD, the AV fistula (or AV graft) site will be examined for inflammation, infection, or flow abnormalities. When scheduled postdose, injection site examinations will be performed within approximately 20 minutes after completion of the HD session. Reactions will be rated according to the FDA Guidance for Industry: Toxicity Grading Scale for Healthy Adult and Adolescent Volunteers Enrolled in Preventive Vaccine Clinical Trials ([FDA Guidance 2007](#)) as follows:

| Local Reaction | Mild (Grade 1) | Moderate (Grade 2) | Severe (Grade 3) |
|-----------------------|---|---|--|
| Pain | Does not interfere with activity | Repeated use of non-narcotic pain reliever > 24 hours or interferes with activity | Any use of narcotic pain reliever or prevents daily activity |
| Tenderness | Mild discomfort to touch | Discomfort with movement | Significant discomfort at rest |
| Erythema/Redness* | 2.5 – 5 cm | 5.1 – 10 cm | > 10 cm |
| Induration/Swelling** | 2.5 – 5 cm and does not interfere with activity | 5.1 – 10 cm or interferes with activity | > 10 cm or prevents daily activity |

* In addition to grading the measured local reaction at the greatest single diameter, the measurement should be recorded as a continuous variable.

** Induration/swelling should be evaluated and graded using the functional scale as well as the actual measurement.

13.2.6 Bleeding of Access Site

Evaluation of bleeding and bleeding time from the HD vascular access sites on the AV fistula or AV graft using the ladder or buttonhole technique will be performed as per Study Events Flow Chart ([Section 6](#)).

Following hemodialysis, the needle will be removed from the vascular access site and immediately followed by the placement of the dressing (i.e., gauze). Pressure will be applied manually by a clinical associate for 10 minutes before checking for evidence of bleeding around the dressing. If there is still some bleeding, pressure will be applied back at the site for 5 minutes. The site will then be checked again for evidence of bleeding; this procedure will be repeated every 5 minutes until bleeding has stopped. Once bleeding has stopped, a new gauze dressing is applied and then taped. To ensure consistency when applying the pressure, the clinical staff will have received adequate training and an attempt will be made to have the same associates perform this test.

The time to clot will be recorded.

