### **8.10 Bleeding Time**

The time to clot (bleeding time) will be recorded following hemodialysis after the needle is removed from the vascular access site on Days -7, -5, -3, 1, 3, 5 and 12. Summary statistics will be calculated for time to clot by treatment and assessment timepoint.

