Appendix 16.2.5.8.2 Dialyzer Assessment (II of V) (Safety Population)

Dose Level/ Placebo	Subject Number	Day	Hour	Atrial Pressure		Venus Pressure		Blood Flow Rate mL/min	Time to Hemostasis		Dialysis Filter Collected*?
				Time	mmHg	Time	mmHg		Time	Length (min)	
XXX <units>	X	X	X	HH:MM	XX	HH:MM	XX	XX	HH:MM	XX	Yes

Note: 0.25 mg/kg: Single IV Infusion of 0.25 mg/kg xisomab 3G3  
 0.5 mg/kg: Single IV Infusion of 0.5 mg/kg xisomab 3G3  
 Placebo = pooled placebo  
 \* Was the dialysis fi lter collected, sealed and stored < -20 C until shipment?

Program: /AAXXXX/ECR/sas\_prg/stsas/lis\_PROGRAMNAME.sas DDMMYYYY HH:MM

Appendix 16.2.5.8.3 Dialyzer Assessment (III of V) - Number and Volume of Saline Flushes (Safety Population)

Dose Level/ Placebo	Subject Number	Day	Hour	Saline Flush Number	Time of Flush	Volume (mL)	Total Volume of Flushes (mL)	Total Number of Flushes
XXX <units>	X	X	X	1	HH:MM	XX	XXX	XX
				2	HH:MM	XX		
				3	HH:MM	XX		
				4	HH:MM	XX		
				5	HH:MM	XX		
				6	HH:MM	XX		

Note: 0.25 mg/kg: Single IV Infusion of 0.25 mg/kg xisomab 3G3  
 0.5 mg/kg: Single IV Infusion of 0.5 mg/kg xisomab 3G3  
 Placebo = pooled placebo

Program: /AAXXXX/ECR/sas\_prg/stsas/lis\_PROGRAMNAME.sas DDMMYYYY HH:MM

Aronora, Inc.  
 xisomab 3G3, Protocol 3G3-18-02  
 Celerion, Clinical Study Report No. CA23900

---

Appendix 16.2.5.8.4 Dialyzer Assessment (IV of V) - Clotting in the Drip Chamber (Safety Population)

Dose Level/ Placebo	Subject Number	Day	Hour	2 Hours after Start of Dialysis					End of Dialysis						
				Time	Category*					Time	Category*				
					1	2	3a	3b	4		1	2	3a	3b	4
XXX <units>	X	X	X	HH:MM	X	X	X	X	X	HH:MM	X	X	X	X	X

Note: 0.25 mg/kg: Single IV Infusion of 0.25 mg/kg xisomab 3G3

0.5 mg/kg: Single IV Infusion of 0.5 mg/kg xisomab 3G3

Placebo = pooled placebo

\*Category:1=No detectable clotting, 2=Presence of fibrinous ring or minimum clot affecting less than 5% of chamber space,  
 3a=Clot formation (affecting more than 5% of but less than 30% of chamber space) but dialysis still possible,  
 3b=Clot formation (affecting more than 30% of chamber space) but dialysis still possible,  
 4=Complete occlusion of chamber

Program: /AAXXXXX/ECR/sas\_prg/stsas/lis\_PROGRAMNAME.sas DDMMYYYY HH:MM

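### Access-site bleeding time is left-censored at 10 minutes and read in 5-minute steps, but the SAP summarises it as an exact time and drops the planned incidence of bleeding

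*Protocol*

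**What the plan says.** Protocol 13.2.6 sets the measurement. After needle removal and dressing, "Pressure will be applied manually by a clinical associate for 10 minutes before checking for evidence of bleeding around the dressing". If the site still bleeds, pressure is reapplied for 5 minutes and the site is checked again; "this procedure will be repeated every 5 minutes until bleeding has stopped". The section ends: "The time to clot will be recorded". It does not say what to enter when the site is already dry at the first check.

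Protocol 9.2 places the measure in the primary outcome, judged against pre-treatment and placebo, alongside "vascular access site reaction, bleeding time, and changes in vital signs, ECGs, and clinical laboratory evaluations" (the run includes bleeding time itself). Protocol 14.3.1 plans to count both the incidence and the time of access-site bleeding and to compare them with pre-treatment, placebo and post-treatment.

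SAP 8.10 says: "Summary statistics will be calculated for time to clot by treatment and assessment timepoint". SAP 8 defines the statistics for continuous safety variables as n, mean, SD, minimum, median and maximum. The programmer note in SAP 11.3 gives bleeding time one column per treatment on the pattern of Table 11-4, whose footnote specifies arithmetic means. The listing in Appendix 16.2.5.8.2 has a "Time to Hemostasis" field with a clock time and a length in minutes, and no censoring flag. SAP 8.10 has no incidence, although SAP 9 names only the length of dialysis and the timing of the BUN and potassium samples as changes and otherwise calls the analyses aligned with the protocol.

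**The concern.** Followed as written, the procedure cannot tell a site that stopped at 2 minutes from one that stopped at 9. Both are first seen dry at 10 minutes. A mean of such readings is held up by the floor and its SD is compressed. If most patients stop before the first check, the table shows values at or near 10.0 with a small SD in every arm, which looks like precise evidence of no effect but may only reflect the checking rule.

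This matters because the case for the drug is anticoagulation without the bleeding risk of heparin (Protocol 8.4.1), while Protocol 8.5 concedes that its haemostatic safety in these patients is not yet known. Access-site bleeding is the scheduled, timed bleeding measure, taken on seven dialysis days. The SAP deals with comparable data properly elsewhere: it has a rule for drug concentrations below the quantitation limit and tabulates clotting by ordered category. Bleeding time gets neither.

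**Working it through.** The documents give no bleeding-time distribution, effect size, alpha or power, so there is no figure of the plan's own to reproduce.

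**Inputs from the documents.** First check at 10 minutes and re-checks every 5 (Protocol 13.2.6). Cohorts of 9–12 randomised 2:1 (Protocol 14.1), which gives 6–8 active per dose and 3–4 placebo per cohort, or 6–8 when placebo is pooled.

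**Reading rule.** For true time t, reading = 10 if t ≤ 10; otherwise 10 + 5 × ceil((t − 10)/5). Entering a dry first check as 10 is an inference, since the protocol does not state the entry.

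**Step 1: one patient, true time doubled.**

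| True time (min) | Reading before | Reading after doubling |
|---|---|---|
| 2, 3, 4 or 5 | 10 | 10 |
| 6 or 7 | 10 | 15 |
| 8, 9 or 10 | 10 | 20 |
| 12 | 15 | 25 |

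A doubling is fully hidden exactly when 2t ≤ 10, that is t ≤ 5. Above that, the reading rises by at least 5 minutes.

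**Step 2: group means, under an assumed distribution.** Assumption, not in the documents: lognormal true times with median m and log-SD s.

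- P(reading = 10) = Φ(ln(10/m)/s).
- Mean reading = 10 × P(t ≤ 10) + Σ (10 + 5k) × P(5 + 5k < t ≤ 10 + 5k), k = 1, 2, …
- Example, s = 0.5: for m = 4, Φ(0.916/0.5) = 0.967; for m = 8, Φ(0.223/0.5) = 0.672.

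| Median doubles | log-SD | Share reading 10 | Mean reading |
|---|---|---|---|
| 4 → 8 | 0.3 | 99.9% → 77% | 10.0 → 11.2 |
| 4 → 8 | 0.4 | 99% → 71% | 10.1 → 11.8 |
| 4 → 8 | 0.5 | 97% → 67% | 10.2 → 12.4 |
| 6 → 12 | 0.3 | 96% → 27% | 10.2 → 15.0 |
| 6 → 12 | 0.4 | 90% → 32% | 10.6 → 15.6 |
| 6 → 12 | 0.5 | 85% → 36% | 11.0 → 16.3 |

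The expected recorded median stays at 10 whenever the true median is below 10, because more than half the readings then sit at the floor.

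**Step 3: how much information is lost.** The SAP plans no test; a two-sided 5% t-test serves only as a yardstick, over 4,000 simulated comparisons of 6 v 6 and of 8 v 8 patients at log-SD 0.4. For 4 → 8 minutes, exact times would show the difference in 77–89% of comparisons and the protocol readings in 13–14%; the group medians are identical in 78–83%. For 6 → 12 minutes the figures are 76–90% with exact times and 52–70% with the readings.

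**The case against.** A reader might infer that any doubling of a short bleeding time would go unseen. The documents do not support that. Times above 5 and up to 10 minutes are also below the floor, yet doubling them moves the reading to 15 or 20. With no distribution given, nobody can say from the documents which case applies. This objection stands, and it limits the point.

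The planned output also has more than the mean. SAP 8 reports the maximum. In the 4 → 8 case at log-SD 0.5, the chance that at least one of 6–8 active patients reads above 10 in a session is 1 − 0.672^6 to 1 − 0.672^8 = 91–96%, against 1 − 0.967^6 to 1 − 0.967^8 = 18–24% in the comparison group. The listing shows each patient's length. Bleeding adverse events are collected too, so bleeding time is not the only window on haemostasis. All of this stands. But a maximum and a listing do not replace a summary of how many patients were still bleeding.

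The analysis is descriptive, and neither document commits to a conclusion of no prolongation. That is true; the risk lies in how the table will be read. Finally, re-tabulation recovers nothing below 10 minutes, because that loss comes from the checking schedule. This is correct, and is why the report needs a statement of the limit. Staff might also enter other minutes than the schedule yields, but readings would then mix two rules, which equally calls for a stated convention.

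**Conclusion.** The point holds in a limited form. The floor and the 5-minute steps follow from Protocol 13.2.6 alone. The SAP treats the readings as exact, has no rule for a site dry at the first check, and leaves out the planned incidence.

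The size is conditional. For a true time of 5 minutes or less, a doubling leaves the reading unchanged. At an assumed median of 4 minutes it moves the recorded mean by about 1 to 2 minutes; at 6 minutes it moves it by about 5, which would be visible. These group figures rest on the lognormal assumption with log-SD 0.3–0.5, on the schedule being followed, and on a dry first check being entered as 10. The point does not show that the trial would miss a bleeding effect. It shows that a flat mean with a small SD would not be evidence against one. It should be corrected before the analysis is run.

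**What to change.** In SAP 8.10 and its table shell:

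- Record and analyse each reading as an interval: ≤10, >10–15, >15–20 minutes and so on. A site dry at the first check is entered as ≤10, not 10.
- Tabulate, by arm and day, the number stopped at each check, in place of the mean and SD.
- Report the share still bleeding at the first check, with its difference from pooled placebo and from pre-treatment. Protocol 14.3.1 does not define its incidence of bleeding, but this share is a natural reading of it and would restore the omitted item.
- State in the study report that changes within the first 10 minutes cannot be detected.

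The cost is SAP wording, one table shell and a CRF entry convention. The shell needs attention anyway: SAP 11.1 sources the in-text bleeding-time table (Table 12-5) to the coagulation and platelet table 14.3.5.5, and SAP 10.2 lists no bleeding-time table. The bedside procedure is unchanged. What is given up is strength of claim, since any statement of no effect on bleeding time becomes more modest.
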